## 6.0 TRIAL FLOW CHART

## 6.1 Study Flow Chart

Trial Period:	Screening Phase		Pembrolizumab Treatment Cyclesa								End of Treatment	Post-Treatment													
	Treatment Cycle/Title:	Pre-screening (Visit 1)	Main Study Screening (Visit 2)	1	2	3	4	To be repeated up to 16 cycles				Discon	Safety Follow-up	Follow Up Visitsb	Survival Follow-Up										
Scheduling Window (Days) c :		-28 to -1		± 3	± 3	± 3	± 3	± 3	± 3	± 3	At time of Discon	30 days post discon	Every 12 weeks post discon	Every 12 weeks											
HIV 1 and 2 antibody		X																							
CBC with Differential k		X		X	X	X	X	X	X	X		X	X	X											
Comprehensive Serum Chemistry Panel k		X		X	X	X	X	X	X	X		X	X	X											
Urinalysis		X					X					X													
T3, FT4 and TSH		X			X		X		X			X l	X												
Quantitative immunoglobulins: IgG, IgA and IgM		X					X m					X	X												
Bone Marrow Biopsy and Aspirate		X n																							
Efficacy Measurements																									
Chest X Ray, PA and Lateral		X																							
CT Neck, Chest, Abdomen and Pelvis o							X p						X												
PET-CT o		X					X p			X		X q													
Bio-Marker Studies																									
Archival or Newly Obtained Tissue Collection (optional) r		X					X r																		
Correlative Studies Blood Collection (optional) r		X	X	X			X																		
*For patients treated with 22 fractions of EBRT, cycle#2 of pembrolizumab will occur during EBRT																									

a. In general, assessments/procedures are to be performed on Day 1 and prior to the first dose of treatment for each cycle unless otherwise specified. Treatment cycles are 3 weeks (21 days); however the treatment cycle interval may be increased due to toxicity according to the dose modification guidelines provided in Section 5.2.1.2. If the interval is increased, all procedures except for response assessment should be performed based on the new dosing schedule.

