- b. In subjects who discontinue study therapy without documented disease progression, every effort should be made to continue monitoring their disease status as per the follow-up schedule until (1) the start of new anti-cancer treatment, (2) documented disease progression, (3) death, or (4) the end of the study, whichever occurs first.
- c. In general, the window for each visit is  $\pm$  3 days unless otherwise noted.
- d. Written consent must be obtained prior to performing any protocol specific procedure. Results of a test performed prior to the subject signing consent as part of routine clinical management are acceptable in lieu of a screening test if performed within the specified time frame (e.g., within 28 days prior to the first dose of trial treatment). Screening number will be assigned when the study informed consent is signed.
- e. Prior medications – Record all medications taken within 28 days of screening visit. Concomitant medications – Enter new medications started during the trial through the Safety Follow-up visit. Record all medications taken for SAEs as defined in Section 7.2.
- f. For patients treated for aggressive NHL, cycle#2 of pembrolizumab will occur during EBRT
- g. AEs and laboratory safety measurements will be graded per NCI CTCAE version 4.0. All AEs, will also be evaluated for seriousness. Record all AEs occurring within 30 days after the last dose of trial treatment. Report all SAEs (related and unrelated to trial treatment) and ECIs occurring up until 90 days after the last dose of trial treatment or the start of new anti-cancer treatment, whichever comes first. Afterwards, report only SAEs and ECIs that are related to trial treatment.
- h. Vital signs to include temperature, pulse, respiratory rate, weight and blood pressure. Height will be measured at visit 1 only.
- i. For women of reproductive potential, a urine pregnancy test should be performed within 72 hours prior to first dose of trial treatment. If urine pregnancy results cannot be confirmed as negative, a serum pregnancy test will be required.
- j. Coagulation factors (PT/INR and aPTT) should be tested as part of the screening procedures for all subjects. Any subject receiving anticoagulant therapy should have coagulation factors monitored closely throughout the trial.
- k. After Cycle 1, lab samples can be collected up to 72 hours prior to the scheduled time point. See Section 7.1.3 for details regarding laboratory tests.

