### **7.1.3 Laboratory Procedures/Assessments**

Details regarding specific laboratory procedures/assessments to be performed in this trial are provided below in the Laboratory Safety Evaluations Section (Hematology, Chemistry and Urinalysis). Laboratory tests for hematology, chemistry, urinalysis, and others are specified in Table 5.

Laboratory tests for screening or entry into the trial should be performed within 28 days prior to the first dose of treatment. CBC with differential and serum chemistry panel will need to be repeated if screening tests were performed more than 7 days prior to the first dose of pembrolizumab as detailed under Trial Flow Chart. After Cycle 1 of pembrolizumab, pre-dose laboratory procedures can be conducted up to 72 hours prior to dosing. Results must be reviewed by the investigator or qualified designee and found to be acceptable prior to each dose of trial treatment.

The schedule for laboratory assessments is provided under the Trial Flow Chart. CBC with differential should include total white count, absolute neutrophil count, absolute lymphocyte count, hemoglobin, and platelet count. Comprehensive serum chemistry panel should include sodium (Na), potassium (K), chloride (Cl), glucose, bicarbonate (CO2), blood urea nitrogen (BUN), creatinine (Cr), calcium (Ca), magnesium (Mg), phosphorus, total protein, albumin, alkaline phosphatase, aspartate transaminase (AST), alanine transaminase (ALT), total bilirubin, uric acid, and lactate dehydrogenase (LDH). Direct bilirubin should be obtained if total bilirubin is above the upper limit of normal. Urinalysis should include blood, glucose, protein, and specific gravity. If blood, glucose, and protein are abnormal on urinalysis, a urine microscopic exam should be performed. Total triiodothyronine (T3) will be performed if TSH is abnormal.

Table 5 Laboratory Tests

Hematology	Chemistry	Urinalysis	Other
Hematocrit	Albumin	Blood	Serum $\beta$ -human chorionic gonadotropin†
Hemoglobin	Alkaline phosphatase	Glucose	( $\beta$ -hCG)†
Platelet count	Alanine aminotransferase (ALT)	Protein	PT (INR)
WBC (total and differential)	Aspartate aminotransferase (AST)	Specific gravity	aPTT
Red Blood Cell Count	Lactate dehydrogenase (LDH)	Microscopic exam ( If abnormal )	Total triiodothyronine (T3)
Absolute Neutrophil Count	Carbon Dioxide ‡	results are noted	Free thyroxine (T4)
Absolute Lymphocyte Count	( $CO_2$ or bicarbonate)	Urine pregnancy test †	Thyroid stimulating hormone (TSH)

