#### **8.2 Statistical Analysis Plan**

Phase II design:

The overall response (OR: complete response + partial response) of non-irradiated lesion(s) at three months and dose limiting toxicity (DLT) at one cycles (3 weeks) will be monitored simultaneously using the Bayesian stopping boundaries calculated based on beta-binomial distributions. Independence is assumed between OR and DLT.

DLT is defined as the following toxicities observed during cycle one of the treatment that are considered by the investigator to be related to therapy:

1. Grade 4 neutropenia (ANC < 500/mm3) lasting more than 7 consecutive days.
2. Grade 3 neutropenia with fever and/or infection, where fever is defined as an oral Temperature  $\geq 38.5^{\circ}\text{C}$ .
3. Grade 4 thrombocytopenia (platelets < 25,000/mm3) lasting more than 7 consecutive Days.
4. Grade 3 thrombocytopenia with clinically significant bleeding.
5. A platelet count < 10,000/mm3 at any time.
6. Grade 3 or greater nausea and/or emesis despite the use of optimal anti-emetic Prophylaxis. Optimal anti-emetic prophylaxis is defined as an anti-emetic regimen that employs a 5-HT3 antagonist given in standard doses and according to standard schedules.
7. Grade 3 or greater diarrhea that occurs despite maximal supportive therapy.
8. Any other Grade 3 or greater non-hematologic toxicity with the following exceptions: Grade 3 arthralgia/myalgia or brief (< 1 week) Grade 3 fatigue.
9. A delay of more than 2 weeks in the initiation of Cycle 2 of treatment because of a lack of adequate recovery of therapy related hematological or non-hematologic toxicities.

In cohort 1 for the patients with multiple sites of aggressive NHL, we will consider that the regimen is promising if the OR rate of the non-irradiated lesion (s) at 3 months is at least 35% and the DLT rate at cycle one is below 30%. A sample size of 20 ensures that, if the trial is not terminated early, a posterior 90% credibility interval for OR rate at 3 months will have width of 0.335 at most, when 7 responses are observed out of the 20 patients, under the assumption of 35% OR rate. The prior probability of OR and DLT for the regimen are modeled by beta distribution ( $\text{Beta}(0.35, 0.65)$  and  $\text{Beta}(0.3, 0.7)$ , respectively). Denoting the probability of OR and DLT by  $\{\theta_{\text{OR}}, \theta_{\text{DLT}}\}$ , and they are compared to fixed targets of OR and DLT rates. The following decision criteria will be applied:

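### The scheduled blood counts cannot reliably establish DLT items 1, 3 and 5, so the DLT rate may be undercounted and the 6-of-10 stop may be less sensitive than tabulated

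*Combined protocol and SAP*

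**What the plan says.** Section 8.2 states that "dose limiting toxicity (DLT) at one cycles (3 weeks) will be monitored simultaneously" with response, and that "DLT is defined as the following toxicities observed during cycle one of the treatment" and judged by the investigator to be related to therapy. Three of the nine items rest on blood counts alone:

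- Item 1: "Grade 4 neutropenia (ANC < 500/mm3) lasting more than 7 consecutive days".
- Item 3: "Grade 4 thrombocytopenia (platelets < 25,000/mm3) lasting more than 7 consecutive" days.
- Item 5: "A platelet count < 10,000/mm3 at any time".

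The resulting DLT count drives one interim rule per cohort (stop at 6 or more DLTs in the first 10 patients). It also drives the criterion that the regimen is promising only if the cycle-one DLT rate is below 30%.

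On blood counts, Section 7.1.3 says: "The schedule for laboratory assessments is provided under the Trial Flow Chart". In Section 6.1 the CBC row has one mark at screening and one per treatment cycle. Footnote a sets the timing: "In general, assessments/procedures are to be performed on Day 1 and prior to the first dose of treatment for each cycle unless otherwise specified". Footnote k adds: "After Cycle 1, lab samples can be collected up to 72 hours prior to the scheduled time point".

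**The concern.** Items 1 and 3 are defined by duration and item 5 by a nadir, so all three call for repeated counts within the cycle. The schedule has none between the start of cycle 1 and the draw before the second dose. The definition and the data collection do not fit each other.

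This rule is the plan's only numerical safety threshold, since the termination criteria in Section 5.10 are qualitative. The operating characteristics in Section 8.2 treat every DLT as seen. An unseen DLT can only lower the observed rate, which makes stopping less likely and the 30% criterion easier to meet. Cytopenia is not remote here: Section 5.1.2 admits patients with an ANC of 1,000 and platelets of 50,000, each only twice the Grade 4 limit in items 1 and 3.

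**Working it through.** **1. When counts are taken.** EBRT starts on Day 1 and pembrolizumab on Day 2 (Sections 2.1 and 5.2.2). The Cycle 1 count is pre-dose. The next scheduled count precedes the second infusion. That infusion is nominally Day 22 on a 21-day cycle, but Day 23 in flow chart footnote r and Section 7.1.2.7. With the 72-hour allowance the draw can fall from Day 19 (22 − 3) to Day 23. The research bloods at Days 9 and 23 are optional and are processed for serum and PBMC, not as a CBC.

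**2. What that one count can show.**
- Items 1 and 3: one low count fits a duration of one day or of two weeks. A normal count on Day 22 fits a Grade 4 episode on Days 8–15, which is 8 days and meets the definition. The scheduled counts alone therefore cannot establish either item.
- Item 5: assume the nadir starts with equal chance on each of Days 2–21 (20 start days). A draw on day c meets a 3-day nadir if it started on day c − 2, c − 1 or c. That gives 3/20 = 15% for a draw on Days 19–21, 2/20 = 10% on Day 22 and 1/20 = 5% on Day 23. For a 7-day nadir the figures are 7/20 = 35%, 6/20 = 30% and 5/20 = 25%. The nadir lengths and the uniform onset are assumptions.

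**3. The plan's own figures.** With the Beta(0.3, 0.7) prior, the posterior probability that the DLT rate exceeds 0.30 is 0.890 at 5 of 10 and 0.969 at 6 of 10, so a boundary of 6 is correct for the 0.95 threshold. Early stopping is

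P(stop) = 1 − P(response bound passed) × [1 − P(X ≥ 6)], with X ~ Binomial(10, DLT rate).

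For cohort 1 at a DLT rate of 0.50 and a response rate of 0.35: P(at least 2 responses in 10) = 0.9140 and P(X ≥ 6) = 0.3770, so P(stop) = 1 − 0.9140 × 0.6230 = 0.4305, as tabulated. All 50 tabulated stopping probabilities reproduce to within 0.00005.

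**4. Effect of missed DLTs.** Let m be the share of DLT patients whose only qualifying event goes unseen. The documents give no value for m, so it is varied. The observed rate is p(1 − m), and P(X ≥ 6) becomes:

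| True rate p | m = 0 | m = 5% | m = 10% | m = 25% |
|---|---|---|---|---|
| 0.50 | 0.377 | 0.317 | 0.262 | 0.128 |
| 0.40 | 0.166 | 0.135 | 0.107 | 0.047 |
| 0.30 | 0.047 | 0.037 | 0.029 | 0.012 |

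For example, p = 0.50 and m = 10% give an observed rate of 0.45 and P(X ≥ 6) = 0.262. The cohort 1 entry of 0.4305 then becomes 0.3759, 0.3250 or 0.2025 for m = 5%, 10% or 25%.

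For the 30% criterion, m = 10% means that a true rate of 0.30/0.90 = 0.333 would on average be observed as 0.30.

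**The case against.** The other side has real points.

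- **Testing is not confined to the schedule.** Section 8.2 counts toxicities that are observed, by whatever test. Section 7.1 allows procedures at unscheduled times if clinically necessary, and Section 7.1.2.1 allows more frequent adverse-event assessment if indicated. Section 5.4 gives 40–50 Gy in fractions of at most 3 Gy, five days a week. That is at least 14 fractions (40/3 = 13.3), so patients are seen almost daily for most of cycle 1.
- **A low Cycle 2 count would be pursued.** Section 7.1.3 requires acceptable results before each dose, and Sections 7.2 and 7.2.3 require outcome follow-up, grade changes and start and stop dates. DLT item 9 counts a Cycle 2 delay of more than two weeks for lack of recovery.
- **Most of the definition is unaffected.** Items 2 and 4 come with fever, infection or bleeding, and items 6 to 8 do not depend on serial counts. The named immune-related toxicities in the dose-modification table include no cytopenia.

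These points rule out the stronger reading that the three items are unobservable. They do not close the gap. A symptomless low count is the least likely to prompt an extra test, and item 9 and outcome follow-up reach only what is still present, or already known, at Cycle 2.

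A reader might also infer that the Cycle 2 count always falls outside the three-week window. The documents do not settle this. It depends on whether the window runs from Day 1 or from the first dose on Day 2, and on the actual draw day, which the 72-hour allowance can bring to Day 21 or earlier.

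**Conclusion.** The point holds in a conditional form. Scheduled counts cannot establish items 1 and 3 and can miss item 5, so the DLT rate may be undercounted. Both the 6-of-10 stop and the 30% criterion may then be less sensitive than Section 8.2 implies. The direction is certain for any event that is missed; the size is not known.

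A reader might go further and conclude that the DLT rate is undercounted by some stated amount. The documents do not support that. They give no frequency for these toxicities and no rate of unscheduled testing, so the table above is a sensitivity range. The absolute loss also shrinks at lower true rates: with 10% missed it is 11.5 points at 0.50, 5.9 at 0.40 and 1.9 at 0.30. Nor is there an error in the stopping boundary or the operating characteristics, which reproduce. This should be fixed, but it does not invalidate the design.

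**What to change.** Reconcile Sections 6.1 and 8.2 so that items 1, 3 and 5 can be evaluated from the counts the trial actually collects. Whether to change the CBC schedule or the wording of the items is for the sponsor to decide. In either case add two statements to Section 8.2:

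1. The Cycle 2 pre-dose CBC belongs to the cycle-one DLT evaluation.
2. How a Grade 4 neutrophil or platelet count of unknown duration enters the DLT tally. One option is to count it as a DLT in the monitoring rule unless a later count shows recovery within 7 days.

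The two statements cost only wording. The downside of the example in (2) is that a few episodes shorter than the definition requires may be counted as DLTs, which makes the rule slightly more cautious. The boundary of 6 in 10 and the tabulated probabilities need no recalculation.

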## 1.0 TRIAL SUMMARY

Abbreviated Title	Pembrolizumab (MK-3475) and radiation for relapsed and refractory Non-Hodgkin Lymphoma
Trial Phase	II
Clinical Indication	Refractory Non-Hodgkin Lymphoma
Trial Type	Treatment (Interventional)
Type of control	Historical Control
Route of administration	Intravenous and external beam radiation
Trial Blinding	Unblinded, open label
Treatment Groups	MK-3475 200 mg every 21 days with concurrent External beam radiation therapy (EBRT)
Number of trial subjects	21
Estimated enrollment period	20 months
Estimated duration of trial	48 months
Duration of Participation	1.5 years
Estimated average length of treatment per patient	24 months

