### **5.3 Randomization or Treatment Allocation**

This is an unblinded, non-randomized trial among patients with relapsed and refractory aggressive NHL. Trial enrollees will receive MK-3475 concurrent with fractionated EBRT. Patients will be stratified according to extent of disease included in the radiation therapy field(s) as follows:

- 1) Cohort 1: Relapsed/Refractory Aggressive B-cell lymphoma with disease excluded from the Radiation Therapy Field (n=20)
- 2) Cohort 2: Relapsed/Refractory Aggressive B-cell lymphoma with all sites of radiographically evident disease treated in 1-2 radiation therapy field(s). Disease (n=20)

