### **5.9 Subject Replacement Strategy**

Additional subjects may be enrolled to ensure that the required number of evaluable subjects is achieved in the applicable analysis population.

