### **8.0 STATISTICAL ANALYSIS PLAN**

#### **8.1 Statistical Analysis Plan Summary**

This is an investigator initiated, open label, phase II clinical trial to evaluate the efficacy of the combination therapy of Pembrolizumab and fractionated external beam radiotherapy (EBRT) in patients with relapsed and refractory aggressive Non-Hodgkin lymphoma (NHL). The maximum number of patients that will be recruited for the study is 40.

The primary objective of the trial is to determine the overall response rate of Pembrolizumab and fractionated EBRT in patients with relapsed and refractory NHL. The secondary objectives are to evaluate the safety, CRR, PFS, OS and duration of response of pembrolizumab with concurrent fractionated EBRT. Patients will receive 200 mg IV of Pembrolizumab with concurrent EBRT at standard of care doses of 40-50 Gy of EBRT in fractions of  $\leq 3$  Gy.. The trial enrollment will be stratified according to the extent of relapsed/refractory disease included in the RT field(s) with 2 cohorts of patients enrolled based on the treated RT field. For Cohort 1, patients with aggressive NHL, will receive RT to 1-2 region(s) of disease and the ORR will be determined for a designated “unirradiated” lesion (Cohort 1). For patients with relapsed/refractory aggressive NHL in Cohort 2, RT will be administered to encompass all sites of radiographically evident disease in 1-2 RT plan(s), the ORR will be based on the disease treated within the RT field. **The maximum number of patients in each cohort is 20 with a total anticipated trial enrollment of 40 patients..**

Overall response rates to PD-1 blockade monotherapy among patients with hematologic malignancies is based on published data. For cohort 1, we assume that concurrent external beam radiation therapy with concurrent pembrolizumab will improve ORR (of the non-irradiated lesion[s]) over the reported rates of PD-1 blockade which are roughly 26% for B cell lymphoma and 17% for T cell lymphoma.

**While the ORR for definitive RT for patients with de novo aggressive NHL approach 100%, overall response rate to salvage RT for patients with refractory aggressive NHL treated with curative intent has been reported to be 78%, with a 5 year progression free survival rate of 34%. We assume that concurrent EBRT and pembrolizumab will improve the ORR when all sites of known disease are radiated.**

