- 1) Stop if  $\text{Prob}\{\theta_{\text{OR}} < 0.35 \mid \text{data}\} > 0.95$ , and
- 2) Stop if  $\text{Prob}\{\theta_{\text{DLT}} > 0.30 \mid \text{data}\} > 0.95$

Patients will be monitored by a cohort size of 10 according to the following stopping boundaries for OR at 3 months and DLT at cycle one. If the number of responses required for moving the trial to next stage has not been achieved, the patient enrollment will be halted until enough responses observed.

Number of patients evaluated	Stop if <= OR observed	Stop if >= DLT observed
10	0-1	6-10
20	Always stop with this many patients	

The operating characteristics are summarized in the following table (based on simulations from 10,000 trials).

True DLT Rate	True OR Rate	Prob (stop the trial early)	Average number of patients treated
0.1	0.15	0.5444	14.56
	0.25	0.2441	17.56
	0.35	0.0861	19.14
	0.45	0.0234	19.77
	0.55	0.0046	19.95
0.2	0.15	0.5472	14.53
	0.25	0.2488	17.51
	0.35	0.0918	19.08
	0.45	0.0295	19.71
	0.55	0.0108	19.89
0.3	0.15	0.5659	14.34
	0.25	0.2798	17.20
	0.35	0.1292	18.71

	0.45	0.0695	19.31
	0.55	0.0516	19.48
0.4	0.15	0.6201	13.80
	0.25	0.3697	16.30
	0.35	0.2379	17.62
	0.45	0.1856	18.14
	0.55	0.1700	18.30
0.5	0.15	0.7161	12.84
	0.25	0.5290	14.71
	0.35	0.4305	15.69
	0.45	0.3914	16.09
	0.55	0.3798	16.20

In cohort 2 patients will be treated to all sites of relapsed or refractory NHL that can be completely included in 1-2 RT field(s), we will consider that the regimen is promising if the OR rate of the radiated disease at 3 months is at least 90% and the DLT rate at cycle one is below 30%. A sample size of 20 ensures that, if the trial is not terminated early, a posterior 90% credibility interval for OR rate at 3 months will have width of 0.203 at most, when 18 responses are observed out of the 20 patients, under the assumption of 90% OR rate. The prior probability of OR and DLT for the regimen are modeled by beta distribution (*Beta*(0.9,0.1) and *Beta*(0.3,0.7), respectively). Denoting the probability of OR and DLT by  $\{\theta_{OR}, \theta_{DLT}\}$ , and they are compared to fixed targets of OR and DLT rates. The following decision criteria will be applied:

- 1) Stop if  $\text{Prob}\{\theta_{OR} < 0.90 \mid \text{data}\} > 0.95$ , and
- 2) Stop if  $\text{Prob}\{\theta_{DLT} > 0.30 \mid \text{data}\} > 0.95$

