## ANALYSIS PLANS

For each patient cohort, summary statistics will be provided for continuous variables such as age. Frequency tables will be used to summarize categorical variables such as gender, histology, response, toxicity type and severity. Response rate and its 95% confidence interval will be estimated for each patient cohort separately. The distribution of time-to-event endpoints, such as time to progression and overall survival, will be estimated using the method of Kaplan and Meier. Comparison of time-to-event endpoints by important patient characteristics will be made using the log-rank test.

Time-to-event outcomes, including PFS and OS will be estimated using the Kaplan-Meier method, with analysis beginning at the receipt of the first dose of MK-3475. The log-rank test will be performed to test the difference in time-to-event distributions between patient groups. Cox proportional hazards model may be used to include multiple covariates in the time-to-event analysis.

Assuming an accrual rate of 2 patients per month, we anticipate an accrual period of roughly 20 months. Data from all subjects who receive any study drug will be included in the safety

analyses. Subjects who entered the study and did not take any of the study drug and had this confirmed, will not be evaluated for safety.

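### The Trial Summary's 21 subjects contradicts the planned 40, and the Cohort 2 interval width of 0.203 is the value at 18 of 20 responses, not an upper bound

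*Combined protocol and SAP*

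**What the plan says.** **Trial size.** In the Trial Summary (section 1.0), the row "Number of trial subjects" has the value 21, and the enrolment period is 20 months. Section 5.3 describes "Cohort 1: Relapsed/Refractory Aggressive B-cell lymphoma with disease excluded from the Radiation Therapy Field (n=20"), and gives Cohort 2 the same size. Section 8.1 states: "The maximum number of patients in each cohort is 20 with a total anticipated trial enrollment of 40 patients". The Analysis Plans part of section 8.2 adds: "Assuming an accrual rate of 2 patients per month, we anticipate an accrual period of roughly 20 months".

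**Precision.** Section 8.2 justifies the Cohort 2 sample size by saying that 20 patients *ensures*, provided the cohort is not stopped early, that the posterior 90% credible interval for the response rate "will have width of 0.203 at most, when 18 responses are observed out of the 20 patients", assuming a 90% rate. The prior is Beta(0.9, 0.1), and the cohort stops at its single interim look if 6 or fewer of the first 10 respond. For Cohort 1 the parallel sentence reads: "interval for OR rate at 3 months will have width of 0.335 at most, when 7 responses are observed out of the 20 patients". There the prior is Beta(0.35, 0.65), and the cohort stops if 0 or 1 of the first 10 respond.

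**The concern.** The Trial Summary total cannot hold two cohorts of 20, so a reader who takes the trial's size from the summary gets about half the planned enrolment.

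The width sentences are worded as guarantees, but a credible interval's width depends on the number of responses observed. In a beta-binomial model it grows as the observed proportion moves from 90% towards 50%. A width calculated at 18 of 20 therefore cannot cap the width at 17, 16 or fewer. The sentence is the precision argument given for 20 patients in Cohort 2, so a reader who takes it at face value will expect more precision than the design assures.

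**Working it through.** **Trial size.** 20 + 20 = 40 (section 5.3), which matches the stated maximum in section 8.1. Accrual: 2 per month × 20 months = 40. At the same rate 21 subjects would need 21 / 2 = 10.5 months, against the Trial Summary's own 20 months. Every figure except the 21 fits 40.

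**Reproducing the plan's widths.** With x responses in 20, the Cohort 2 posterior is Beta(0.9 + x, 0.1 + 20 − x). The equal-tailed 90% interval runs from its 5th to its 95th percentile.

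- At x = 18: Beta(18.9, 2.1), interval 0.7769 to 0.9798, width 0.2029, which rounds to the plan's 0.203.
- The highest-density interval at 18 of 20 has width 0.184, so the plan used equal tails.
- Cohort 1 at x = 7: Beta(7.35, 13.65), width 0.3346, which rounds to the plan's 0.335.

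**Is 0.203 a maximum?** Continuing requires at least 7 responses in the first 10, so final counts of 7 to 20 are possible.

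| Responses of 20 (Cohort 2) | Equal-tailed 90% width |
|---|---|
| 20 | 0.028 |
| 19 | 0.144 |
| 18 | 0.203 |
| 17 | 0.244 |
| 16 | 0.275 |
| 15 | 0.299 |
| 14 | 0.318 |
| 12 | 0.342 |
| 10 | 0.351 (maximum) |
| 7 | 0.340 |

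Every count from 7 to 17 exceeds 0.203; only 18, 19 and 20 do not. Interval type does not matter here: the highest-density width at 17 of 20 is 0.232, also above 0.203.

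**How often at the assumed 90% rate?** Let b(k) be the binomial probability of k responses in 10 at rate 0.90. The probability of passing the response look is b(7) + b(8) + b(9) + b(10) = 0.0574 + 0.1937 + 0.3874 + 0.3487 = 0.9872. Given passing:

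- 17 of 20: 2 × [b(7)b(10) + b(8)b(9)] / 0.9872 = 0.1926
- 16 of 20, summed the same way: 0.0870
- 15 or fewer: 0.0347

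The sum is 0.1926 + 0.0870 + 0.0347 = 0.3143. The plan assumes toxicity to be independent of response, so stopping for toxicity does not alter this conditional figure.

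**At a 78% rate.** Section 8.1 notes that "overall response rate to salvage RT for patients with refractory aggressive NHL treated with curative intent has been reported to be 78"%. At that rate 0.841 of cohorts pass the response look, and of those 0.2113 (17) + 0.2423 (16) + 0.3668 (15 or fewer) = 0.820 exceed 0.203. The most likely final count is 16, with width 0.275.

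**Cohort 1.** Counts of 8 to 13 give widths above 0.335. The largest is 0.351 at 10 of 20, an excess of 0.351 − 0.335 = 0.016.

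**The case against.** The sentence in section 8.2 names its condition, 18 responses of 20 under a 90% rate, and the number is correct for that result. So nothing was miscalculated, and a reader who infers an arithmetic error would be mistaken. But the condition cannot rescue the guarantee. At one fixed result the width is a single value, so *ensures* and *at most* have meaning only as a bound, and as a bound the statement is false.

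It is also fair to say that little depends on the width. No stopping or success rule uses it, and the Analysis Plans text commits to a response rate with a 95% confidence interval, not a 90% credible interval. The very wide intervals are remote at the assumed rate: 12 or fewer responses has probability of about 0.0001 at 90%. The Cohort 1 excess is negligible. All of this stands and limits the importance of the point.

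Two stronger readings are tempting and unsupported. One is that precision is worst near the 78% salvage-radiotherapy rate. The interval is wider there than at 90%, but it is widest near 50%. The other is that the interval must separate the result from 78%. Section 8.1 assumes an improvement over salvage radiotherapy, but the rule in section 8.2 compares the response rate only with 0.90.

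On 21 against 40, the other side can say that the statistical sections agree with one another and no analysis depends on 21. That is so. It makes this a correction to the summary, not doubt about the planned size.

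**Conclusion.** Both statements are wrong as written. The Trial Summary's 21 conflicts with the cohort sizes, the stated maximum and the accrual arithmetic, all of which give 40. The Cohort 2 figure of 0.203 is correct at 18 of 20 but is not a bound: the maximum is 0.351, the adjacent results of 17 and 16 give 0.244 and 0.275, and about 31% of cohorts passing the response look would exceed 0.203 even if the true rate is 90%. These figures rest on the plan's prior, equal-tailed intervals, the stated response boundary at 10 patients, and independence of response and toxicity. Cohort 1 needs the same wording change, but its excess of at most 0.016 has no practical weight. A reader might infer that 20 per cohort is inadequate or that the stopping design is faulty. Neither follows: the recalculation reproduces the plan's widths, and the boundaries and operating characteristics do not depend on them.

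**What to change.** 1. Trial Summary, section 1.0: change the number of subjects from 21 to 40 (20 per cohort).
2. Section 8.2, Cohort 2: replace the guarantee with a conditional statement, for example: *with 20 patients, the width of the 90% credible interval would be about 0.203 if 18 of 20 respond, 0.244 if 17 and 0.275 if 16, and at most 0.351*.
3. Section 8.2, Cohort 1: likewise, *about 0.335 if 7 of 20 respond, and at most 0.351*.

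The cost is one table cell and two sentences. Sample size per cohort, stopping boundaries and operating-characteristic tables stay as they are.
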